Transverse needling is a recently described technique in the treatment of stable

vitiligo. It is believed to induce pigmentation in treated areas by physically moving

melanocytes from pigmented edges of the lesions into depigmented marginal areas

using a horizontal needle moving within the skin tangentially between the two zones.^(17, 18)

AIM OF THE WORK

The aim of this study is to evaluate the effectiveness and tolerability of autologous punch minigrafting, transverse needling technique or combination of both followed by narrow band ultraviolet B phototherapy (311 nm) in the treatment of patients with stable non-segmental vitiligo lesions.

PATIENTS

This study will be carried out on twenty patients having non segmental vitiligo recruited from the attendants of the dermatology and phototherapy outpatient clinics of the dermatology, venereology and andrology department, faculty of medicine, Alexandria University.

Approval of the medical ethics committee of Alexandria Faculty of Medicine will be obtained. An informed written consent for participation in the study and photography will be taken from every participant included in the study after full explanation of the study protocol.

❖ Inclusion criteria:

- Adult patients (>16 years old) of either gender having stable non segmental vitiligo, that is resistant to other lines of repigmentation therapy.
- Stability will be defined in terms of ;^(14,19,20)
 - Lack of progression of old lesions with the past 6 months.
 - No development of new lesions within the same period.
 - Absence of history of koebner phenomenon.
 - Absence of confetti lesions or hypopigmented lesions within the past 6 months.
 - Presence of repigmentation of depigmented areas by medications or spontaneously in the past 6 months.

- While resistance to therapy will be judged after receiving standard protocol of NB-UVB together with oral mini pulse dexamethasone at a dose of 2.5 mg on two consecutive weekly days for 3 months.⁽²¹⁾
- Patients having lesions showing absence (0%) or poor (<25% according to VASI score) repigmentation after this regimen will be considered resistant to medical repigmentation and indicated to surgery. ^(22,23)

Exclusion criteria:-

- Cases of active, progressive disease lacking criteria of stability previously mentioned.
- Patients with segmental or universal vitiligo covering more than 70% body surface area.

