- Patients with known associated autoimmune diseases, bleeding tendency, current or history of skin neoplasia, photosensitive disorders or any contraindications to corticosteroids therapy.
- Patients with tendency towards hypertrophic scars or keloid formation.
- Pregnant female and lactating mothers.
- Patients with emotional and psychological instability.

METHODS

All included patients will be subjected to:

- History taking focusing on duration of the disease, age at onset , progression, site of lesions, number ,date and site of last activity of the affected lesions.
- Family history , previous medications and response to them and general medical history
- General clinical examination and determination of skin phototype.
- Dermatological examination for confirmation of the diagnosis.
- Base line VASI scoring.
- VETF scoring using wood's light examination.
- Base line standardized photography for the lesions.

For each included patient in the study, three main lines of surgical treatment will be used in different areas and compared to a non-surgically treated areas as control.

LINE 1; Autologous punch mini grafts:⁽²⁴⁾

Under local anesthesia, multiple 1mm holes will be made in the depigmented treatment area using 1mm punch graft instrument inserted to a depth of 2-4 mm to remove a small column of depigmented skin that is to be discarded. The punches will be situated at or very close to the border of the lesion to avoid leaving an achromic fissure and will be separated by 5-8 mm distance from each other.

On the donor area mostly is the gluteal area, punches will be harvested using the same sized punches very close to each other so that maximum number of grafts can be taken from a small area.

Then the harvested-punch minigrafts will be inserted into the recipient chambers, pressed firmly by saline soaked gauge for hemostasis and secured by sterile strips or a compression bandage if applicable.

LINE 2; Transverse needling technique: (17, 18)

Needling will be done for selected treatment patch using a 30 G disposable insulin syringe, going from the pigmented margins of the lesion into the vitiliginous patch, Position of the needle will be kept close to the dermoepidermal junction and movement will be from normal skin towards the lesion. Needle pricks may lead to oozing of a small drop of blood which will be managed by physical pressure. No dressings will be needed. The procedure will be repeated for selected lesions weekly for a duration of 3 months.

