LINE 3;Punch minigrafts followed by transverse needling:

In a third lesion, punch minigrafts will be done as mentioned in line 1 and will be left to stabilize for 3 months then transverse needling will be done weekly for the margins of the lesion as well as the areas of the punch grafts toward the vitiliginous area.

- A fourth lesion will be chosen as a control lesion, to which no surgical treatment will be attempted.
- All lesions will receive NB-UVB therapy according to standard protocol twice weekly and the patients will continue on the oral mini pulse dexamethasone at 2.5 mg dose for two consecutive days weekly all through the study period.
- All included patients will be followed up for a duration of 6 months following interventions.⁽²⁵⁾
- Follow up will be done by clinical examination, wood's light and serial photography at each follow up visit.
- Clinical assessment of disease severity initially , after 3 months and at end of 6 months using **Vitiligo Area Scoring Index (VASI);**⁽²⁶⁾
For each body region, the VASI will be determined by the product of the area of vitiligo in hand units (which was set at 1% per unit) and the extent of depigmentation within each hand unit–measured patch (possible values of 0, 10%, 25%, 50%, 75%, 90%, or 100%).
The total body VASI will be calculated using the following formula by considering the contributions of all body regions (possible range, 0-100):

$$\text{VASI} = \sum_{\text{All Body Sites}} [\text{Hand Units}] \times [\text{Residual Depigmentation}]$$

- Serial photography will be done to evaluate type, pattern and extent of repigmentation.
- Assessments of repigmentation will be performed by two blinded dermatologists using a 5-point scale; grade 0 (no repigmentation), grade 1

(1%-5%), grade 2 (6%-25%), grade 3 (26%-50%), grade 4 (51%-75%) and grade 5 (76%-100%).⁽²⁷⁾

- Extent of peri punch repigmentation in mm using a ruler.
- Digital assessment of the size of the lesion and of the depigmented versus repigmented area using Adobe photoshop software.
- Patient satisfaction assessment using visual analogue scale (VAS) after treatment period grading as (VAS, 0-10; 0 grade will be defined as “Not satisfied at all” while grade 10 will be defined as “completely satisfied”).⁽²⁷⁾
- Time till appearance of repigmentation will be calculated for each procedure.

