- Possible side effects of the NB-UVB (erythema , itching and burning) , of the systemic steroids (weight gain, increase in blood pressure, insomnia ,acne ,agitation or menstrual disturbances) or of surgery (ecchymosis , scaring , cobble stoning or color mismatching) will be reported.⁽²⁸⁾

ETHICS OF RESEARCH

Research on human or human products:

- ✓ Prospective study: Informed consent will be taken from patients. In case of incompetent patients, the informed consent will be taken from the guardians.
- Retrospective study: Confidentiality of records will be considered
- DNA / genomic material: Informed consent for DNA / genomic test and for research will be taken from patients. No further tests will be carried out except with further approval of committee and patients. If the samples will travel outside Egypt the researcher will be responsible for transportation and security approval.
- All drugs used in the research are approved by the Egyptian Ministry of Health

Research on animal:

- The animal species are appropriate for the test.
- After test, if the animal will suffer, it will be euthanized and properly disposed.
- After operation, it will have a proper postoperative care.

RESULTS

The results of the study will be tabulated and analyzed with the use of appropriate statistical methods and appropriate figures and diagrams in order to fulfill the aim of the work.

DISCUSSION

The results will be discussed in view of achievement of the aim, their significance and their comparison with previous related studies in literature.

REFERENCES

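### Tolerability of the three surgical lines is a stated aim, but the surgical side-effect list has no item for pain, missed sessions, infection, graft loss or the donor site

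*Protocol*

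**What the plan says.** The protocol's Aim of the Work is to "evaluate the effectiveness and tolerability of autologous punch minigrafting, transverse needling technique or combination of both", each followed by phototherapy. Tolerability thus stands beside effectiveness.

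The three lines differ in how they are delivered:

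- Line 1 (grafting): "Under local anesthesia, multiple 1mm holes will be made in the depigmented treatment area". Grafts come from a second site: "On the donor area mostly is the gluteal area, punches will be harvested using the same sized punches very close to each other". No repeat schedule is stated.
- Line 2 (needling): "The procedure will be repeated for selected lesions weekly for a duration of 3 months". Minor bleeding is expected: "Needle pricks may lead to oozing of a small drop of blood which will be managed by physical pressure". Anaesthesia is not mentioned.
- Line 3 (combination): grafting, a 3-month wait, and "then transverse needling will be done weekly for the margins of the lesion" and around the grafts. The number of weeks is not stated.

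The last bullet of Methods lists side effects in three groups. The phototherapy group opens the bullet: "Possible side effects of the NB-UVB (erythema , itching and burning". A group for systemic steroids follows, and the surgical group closes it: "or of surgery (ecchymosis , scaring , cobble stoning or color mismatching) will be reported". The bullet does not say that effects are recorded per lesion. The only patient-reported measure is a 0-10 satisfaction scale taken after treatment, also not stated to be per lesion.

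**The concern.** Each patient carries all three surgical lines and a control lesion, so a difference in tolerability between lines can be seen only through items that can differ between lesions of the same person. Steroid effects cannot. Phototherapy effects are possible in every lesion, because all lesions receive NB-UVB, and the protocol attributes them to the light. That leaves four surgical items.

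Those four omit the dimensions on which the procedures plainly differ: what the procedure feels like, how often it has to be endured, whether patients keep coming for it, whether the graft takes, and what happens at the harvest site. Pain is not named anywhere in the protocol. Burning is listed only under phototherapy, so discomfort of that kind at a needled lesion could be filed there.

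At stake is half of the aim. Session pain or a refused session that is not written down at the time cannot be recovered by any later analysis plan, so this is a question of data collection and belongs in the protocol.

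**Working it through.** The protocol gives no side-effect rates and no figure to reproduce. The check is a count of items, a count of sessions, and one illustration on stated assumptions.

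**1. What each item, listed or missing, can show**

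| Item | Listed as surgical? | Can arise with grafting | Can arise with needling | If absent, the gap favours |
|---|---|---|---|---|
| Ecchymosis | yes | yes | yes | – |
| Scarring | yes | yes | yes | – |
| Cobblestoning | yes | yes | no | – |
| Colour mismatch | yes | yes | probably not | – |
| Procedural pain | no | yes | yes, at every session | needling |
| Sessions refused or stopped | no | little scope if done once | yes | needling |
| Infection | no | yes | yes | unclear |
| Graft loss | no | yes | no | grafting |
| Donor-site effects | no | yes | no | grafting |

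Of the four listed items, one is graft-specific and a second probably so; two apply to both techniques. None of the four covers pain or session burden. Which technique can cause which effect is a reading of the procedures described; the protocol does not assign items to lines. Line 3 includes both procedures, so every gap applies to it.

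**2. Exposure**

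Weekly for 3 months is about 12 to 13 sessions. With 20 patients:

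- Line 2: 20 × 12 = 240 to 20 × 13 = 260 planned sessions.
- Line 1: 20 × 1 = 20 sessions, if grafting is done once per patient. That is an assumption drawn from the absence of a repeat schedule.
- Line 3: one grafting per patient on the same assumption, plus weekly needling of unstated duration.

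**3. Does the list settle the comparison in advance?**

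Take ecchymosis, which can be recorded for a needled lesion. Let p be the risk per session and k the number of sessions, with sessions independent. Both p and independence are assumptions. The chance of at least one recorded event is 1 − (1 − p)^k.

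| p per session | k = 12 | k = 13 |
|---|---|---|
| 1% | 1 − 0.99^12 = 11% | 1 − 0.99^13 = 12% |
| 5% | 1 − 0.95^12 = 46% | 1 − 0.95^13 = 49% |
| 10% | 1 − 0.90^12 = 72% | 1 − 0.90^13 = 75% |

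Even a modest risk per session gives needling a substantial chance of registering on a listed item. The list therefore does not predetermine which line looks better tolerated. It leaves gaps on both sides whose balance is unknown.

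**The case against.** A reader might infer something stronger: that the list holds only graft complications, so needling must come out as better tolerated whatever patients experience. The documents do not support that. Ecchymosis and scarring are listed under surgery without being tied to grafting, the protocol itself expects small bleeds with needling, and repeated sessions give ecchymosis many chances to be recorded. Two of the omissions, graft loss and the donor-site wound, spare grafting.

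Other points on the same side:

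- *The list is not stated to be closed.* True. But there is no item for other adverse events and no general adverse-event clause, so the named effects are all a reader can rely on being collected.
- *The planned session burden is known from the schedule.* True, and the patient already attends twice weekly for phototherapy. What is not known, and is not set to be recorded, is departure from the schedule and the pain of each session.
- *The satisfaction scale may capture burden.* In part. It is taken once treatment has ended, is not stated to be per lesion, and mixes the cosmetic result with the experience of getting there.
- *The protocol does not say that needling is painful or given without anaesthesia.* Correct. Silence on anaesthesia is not a statement that none is used. This is a reason to measure pain, not to assume it.

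These points remove any claim about direction. They leave the incompleteness standing.

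**Conclusion.** The point holds as one of incomplete collection. Tolerability is a named aim, yet the between-line comparison rests on four surgical items, at least one of them specific to grafting, with nothing on pain, refused or stopped sessions, infection, graft loss or the donor site. The lines differ most in just these respects: about 240 to 260 planned needling sessions in Line 2, against 20 grafting sessions in Line 1 if grafting is done once.

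The comparison may be tilted, but neither the direction nor the size of a net bias is established. The conclusion assumes that the list will be followed as written and that cobblestoning, and probably colour mismatch, need a graft. The single grafting session is an inference and affects only the contrast in exposure. The change is worth making before recruitment because missing session-level data cannot be reconstructed.

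**What to change.** Extend the side-effect bullet in Methods, and state that every surgical item is recorded per lesion:

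- a 0-10 pain score at each grafting or needling session;
- the number of needling sessions given, refused or stopped, with the reason;
- infection, graft loss and donor-site effects, the last attributed to the line for which the grafts were harvested.

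Compare the lines within patient on these together with the four existing items. State the number of grafting sessions in Line 1 and the duration of needling in Line 3, so that exposure is known for each line.

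The cost is a few more columns on the visit form and a little more recording at visits patients already attend. No treatment or clinical rule changes.
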